## 6.3 Withdrawal criteria

Subjects are free to withdraw from the study at any time, without prejudice to their continued care. Subjects who withdraw from the study should complete the Early Termination Visit (see [Section 8.3](#)).

Subjects should be withdrawn from the study and will be asked to come back for the SFU Visit 20 weeks after the final dose of IMP if the subject withdraws his/her consent.

Subjects should be withdrawn from IMP and will be asked to come back for all scheduled visits (up to Week 52) and the SFU Visit 20 weeks after the final dose of IMP if any of the following events occur:

1. The Sponsor or a regulatory agency requests withdrawal of the subject.
2. Subject develops an illness that, in the opinion of the Investigator, would interfere with his/her continued participation, if the risk of continuing with IMP outweighs the potential benefit.
3. Subject is noncompliant with the study procedures or medications, which may present a risk to the safety of the subject, in the opinion of the Investigator.
4. Subject uses prohibited concomitant medications, as defined in [Section 7.8.2](#), that may present a risk to the safety of the subject in the opinion of the Investigator and the Medical Monitor.
5. Subject has a clinical laboratory value meeting any of the following criteria:
  - a. Hepatotoxicity as described in [Section 6.3.1](#).
  - b. A laboratory value meeting any of the following criteria:
    - Absolute neutrophil count  $<1.0 \times 10^3/\mu\text{L}$
    - Absolute lymphocyte count  $<0.2 \times 10^3/\mu\text{L}$

Subjects may remain on IMP if the result is transient. A retest is required within 1 to 2 weeks at a scheduled or unscheduled visit. If the repeat absolute neutrophil count or absolute lymphocyte count is still below the allowable values, the subject must be withdrawn from the IMP. If the repeat absolute neutrophil count or absolute lymphocyte count is above the allowable values, the subject may continue to receive IMP.

6. The subject experiences a severe AE, SAE, or a clinically significant change in a laboratory value occurs that, in the opinion of the Investigator, merits the discontinuation of the IMP and appropriate measures being taken.
7. There is confirmation of a pregnancy during the study, as evidenced by a positive pregnancy test (see [Section 12.1.4](#) for more information regarding pregnancies).
8. Subject develops erythrodermic, guttate or generalized pustular form of PSO.

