9. A subject considered as having either a suspected new LTBI or who develops active TB or NTMB infection during the study (including but not limited to, conversion demonstrated by IGRA or other diagnostic means) must be immediately discontinued from IMP, and an ET Visit must be scheduled as soon as possible, but not later than the next regular visit.

---

The subject must be permanently withdrawn if further examinations result in a diagnosis of active TB, or if the subject is diagnosed with LTBI with no initiation of prophylactic treatment, prematurely discontinues prophylactic treatment, or, in the opinion of the Investigator or Sponsor, is noncompliant with prophylactic TB therapy.

Confirmed active TB is an SAE and must be captured in the electronic Case Report form (eCRF) in the SAE Report Form section. As with all SAEs, periodic follow-up reports should be completed as per protocol requirements until such time as the TB infection resolves.

Additional information on TB policies is provided in [Section 12.3.5](#).

10. Subjects with newly diagnosed IBD or with IBD flares during the study must:

- Be referred, as appropriate, to a health care professional treating IBD, such as a gastroenterologist
- Discontinue IMP and be followed-up until resolution of active IBD symptoms

If IBD flares increase in severity or frequency during the study, the Investigator should use clinical judgment in deciding whether the subject should continue on IMP and contact the Medical Monitor and UCB study physician to confirm the subject's suitability for continued participation in the study.

11. Subjects **must be referred** immediately to a mental healthcare professional and may be withdrawn from the study based upon the Investigator's judgment of benefit/risk for:

- a. Active suicidal ideation as indicated by a positive response ("Yes") to Question 4 of the "Since Last Visit" version of the eC-SSRS.
- b. Moderately severe major depression as indicated by a PHQ-9 score of 15 to 19 if this represents an increase of 3 points compared to last visit.

The mental health consultation must be recorded in the subject's source documentation.

12. Subjects **must be referred** immediately to a mental health care professional and must be withdrawn from the study:

- a. Active suicidal ideation as indicated by a positive response ("Yes") to Question 5 of the "Since Last Visit" version of the eC-SSRS.
- b. Any suicidal behavior since the last visit.

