- c. Severe major depression as indicated by a PHQ-9 score  $\geq 20$ .

The mental health consultation must be recorded in the subject's source documentation.

13. Any subject who develops a clinically important infection or recurrent infections not responsive to standard therapy during the study must discontinue IMP until resolution of the infection. The Investigator should use clinical judgement in deciding whether the subject should restart IMP and contact the Medical Monitor and UCB study physician to confirm the subject's suitability for continued participation in the study.

Investigators should contact the Medical Monitor, whenever possible, to discuss the withdrawal of a subject from IMP or from the study in advance.

---

Subjects withdrawing from the study who are not continuing for all scheduled visits, will undergo the ET Visit and the SFU Visit 20 weeks after their final dose of IMP.

Investigators should attempt to obtain information on subjects in the case of withdrawal or discontinuation. For subjects considered as lost to follow-up, the Investigator should make an effort (at least 1 phone call and 1 written message to the subject) and document his/her effort (date and summary of the phone call and copy of the written message in the source documents), to complete the final evaluation. All results of these evaluations and observations, together with a narrative description of the reason(s) for removing the subject, must be recorded in the source documents. The electronic Case Report Form (eCRF) must document the primary reason for withdrawal or discontinuation.

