### **6.3.1 Potential drug-induced liver injury IMP discontinuation criteria**

Subjects with potential drug-induced liver injury (PDILI) must be assessed to determine if IMP must be discontinued. In addition, all concomitant medications and herbal supplements that are not medically necessary should also be discontinued.

The PDILI criteria below require immediate discontinuation of IMP:

- Subjects with either of the following:
  - ALT or AST  $\geq 8$ xULN
  - ALT or AST  $\geq 3$ xULN and coexisting total bilirubin  $\geq 2$ xULN
  - Subjects with ALT or AST  $\geq 3$ xULN who exhibit temporally associated symptoms of hepatitis or hypersensitivity. Hepatitis symptoms include fatigue, nausea, vomiting, right upper quadrant pain or tenderness. Hypersensitivity symptoms include fever (without clear alternative cause), rash, or eosinophilia (ie,  $>5\%$ ).

If a nondrug-related cause for the symptoms can be confirmed, these subjects may resume IMP administration after discussion with the responsible UCB physician, but only when the requirements for rechallenge with IMP as provided in [Section 12.2.1.2.1](#) are followed.

The PDILI criterion below allows for subjects to continue on IMP at the discretion of the Investigator.

- Subjects with ALT or AST  $\geq 5$ xULN and  $<8$ xULN, total bilirubin  $<2$ xULN, and no eosinophilia (ie,  $\leq 5\%$ ), with no fever, rash, or symptoms of hepatitis (eg, fatigue, nausea, vomiting, right upper quadrant pain or tenderness).

Evaluation of PDILI must be initiated as described in [Section 12.2.1](#) with repeat tests performed in 2 weeks. Upon retest, if ALT or AST values have reduced to  $<5$ xULN, the subject can continue with the study. However, if ALT or AST remains  $\geq 5$ xULN  $<8$ xULN after retest, IMP should be temporarily withheld and subject should undergo a repeat test in 2 weeks. The subject will continue to be monitored at least twice per week until values normalize, stabilize, or return to within baseline values. If ALT or AST values remain  $\geq 5$ xULN even after the second retest, then the subject should be permanently withdrawn from the study and should be followed for possible PDILI.

If subjects are unable to comply with the applicable monitoring schedule, IMP must be discontinued immediately.

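### Section 6.3 item 10 stops IMP at any IBD flare, yet leaves continuing on IMP to the investigator when flares worsen or become more frequent

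*Protocol*

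**What the plan says.** The list in Protocol Section 6.3 opens with events for which a subject should be withdrawn from IMP while still attending visits to Week 52 and the safety follow-up visit. Item 10 is one of these events and has two parts.

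- **The bullets.** They begin "Subjects with newly diagnosed IBD or with IBD flares during the study must" and require referral as appropriate, and then "Discontinue IMP and be followed-up until resolution of active IBD symptoms". No severity threshold or exception is given.
- **The following paragraph.** When flares increase in severity or frequency, "the Investigator should use clinical judgment in deciding whether the subject should continue on IMP". The investigator is also to contact the Medical Monitor and the sponsor's study physician about the subject's suitability to stay in the study.

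Item 10 does not mention restarting IMP. Nothing else in the protocol says which part governs. Section 12.1.1.4 names IBD as a safety topic of interest, with referral as appropriate, but gives no dosing rule.

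**The concern.** A subject whose flares are worsening or recurring falls under both parts. The bullets say that IMP must stop. The paragraph asks whether the subject should stay on it. A site could follow the paragraph in good faith and keep dosing through an active, worsening flare, while another site would stop the same subject.

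This is a safety stopping rule, and the trial can expect to use it. Exclusion criterion 13 admits subjects with IBD that is not active at Screening or Baseline, so flares of existing disease can occur.

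Differences between sites would also reach the data. TEAEs leading to withdrawal from IMP are a secondary safety variable (Section 4.2.2). Stopping study treatment before Week 16 is the intercurrent event in the primary estimand and is scored as non-response (Section 14.3.1.1).

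**Working it through.** The plan states no figure here, so the check is of the text. It has three steps, followed by a note on size.

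**1. Which instruction applies to whom.**

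| Situation | Bullets | Following paragraph | Result |
|---|---|---|---|
| Newly diagnosed IBD, no later worsening | Stop | Does not apply | No conflict |
| Single flare that does not worsen | Stop | Does not apply | No conflict |
| Flare that grows more severe while active | Stop | Judge whether to continue | Conflict |
| Flares recurring more often, or each worse than the last | Stop at each one | Judge whether to continue | Consistent only if a restart between flares is assumed |

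**2. Whether item 10 itself supplies the hold-then-judge sequence.** It does not. The words about resolution attach most naturally to the follow-up, not to the stop. The lead-in speaks of withdrawal from IMP, and no restart is mentioned. Item 13, on infections, shows the sequence written out: the subject "must discontinue IMP until resolution of the infection. The Investigator should use clinical judgement in deciding whether the subject should restart IMP". Item 5, on low neutrophil or lymphocyte counts, shows how an exception to a stop is written: "Subjects may remain on IMP if the result is transient", with a retest that decides the matter. Item 10 has neither a restart step nor a condition that lifts its stop.

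**3. Whether word usage elsewhere settles it.** It leans one way but is not decisive.

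- In Section 6.3.1, the liver criterion that needs no immediate stop "allows for subjects to continue on IMP at the discretion of the Investigator". In item 5, after a satisfactory retest "the subject may continue to receive IMP". Both use the verb *continue* for subjects who have not been taken off drug.
- After a liver-related stop, Section 6.3.1 uses a different verb: "these subjects may resume IMP administration after discussion with the responsible UCB physician".
- Against this, footnote b of Figure 12-2 says that subjects with latent TB may *continue* the study after at least 4 weeks of prophylaxis, although Section 12.3.5.4 requires them to stop IMP first. That footnote concerns the study and not IMP, but it shows that the usage is not uniform.

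**Size.** The documents give no IBD or flare rate, so no count can be derived. Per subject, with 420 planned on bimekizumab (Section 14.9):

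- One subject handled differently moves that arm's rate of TEAEs leading to withdrawal by 1/420 = 0.24 percentage points.
- One subject rescored on ACR50 moves that arm's response rate by at most the same 0.24 points, against a planned difference of 27.8 points (Section 14.9.1).

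**The case against.** The strongest reply is that the two parts form a sequence. In this protocol, discontinuing IMP is not always final. Item 13 provides for a restart after an infection. Section 12.2.1.2.1 allows rechallenge after a liver-related stop. Section 12.3.5.4 lets a subject resume after TB prophylaxis has begun. Item 9 separately describes permanent withdrawal. On that view the bullets mean stop and follow to resolution. The paragraph then concerns a pattern of flares over time in subjects who have gone back on drug, and adds an escalation step. Its closing clause on suitability matches the one in item 13, where it plainly follows a stop. Nothing in the paragraph says that the bullets cease to apply, and the discretion is not unsupervised.

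Much of this stands. The sequence is plausible for recurring flares, including later flares that are worse than earlier ones. Sponsor contact also limits how far sites can diverge.

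Two things remain. The sequence is not written, because item 10 has no restart step. It also does not cover a flare that worsens while still active: the bullets already require a stop, and asking whether to continue cannot be a question about restarting. Sponsor contact says whom to call, but not which instruction holds.

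**Conclusion.** The point holds as an internal inconsistency in a safety stopping rule, confined to flares that worsen or become more frequent. It should be corrected for patient safety and consistent conduct. The number affected is probably small, though the documents do not give it. The effect on the primary result is negligible.

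A reader might infer more than the documents support:

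- **That item 10 is defective for all IBD events.** It is not. For newly diagnosed IBD, or a flare that does not worsen or recur, only the stop applies.
- **That the protocol's vocabulary proves continued dosing was intended.** It does not. The usage is mixed, and a hold-then-judge reading remains open.
- **That the withdrawal counts would be materially distorted.** No IBD frequency is given, so any count of affected subjects, or share of expected withdrawals, would be a guess.

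The conclusion rests on the current text of Section 6.3 and on no other section stating which part of item 10 prevails. A statistical analysis plan would not ordinarily settle a dosing rule of this kind.

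**What to change.** Leave the bullets, and the rule for newly diagnosed IBD, as they are. Replace the second paragraph of item 10 with wording such as:

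> IMP must be stopped at every IBD flare, including one that is worsening or more frequent than before. Only once the active symptoms of a flare have resolved may the Investigator judge whether IMP should be restarted, weighing any increase in the severity or frequency of flares. Before any restart the Investigator must contact the Medical Monitor and the sponsor's study physician to confirm that the subject is suitable.

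This makes explicit, for flares only, the restart that the hold-then-judge reading assumes. It adds no restart route for newly diagnosed IBD. If the sponsor intends a different rule, such as permanent withdrawal after a flare or a severity threshold, that should be written instead.

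The cost is one paragraph of wording, with the approvals that Section 15.5 requires for an amendment, and possibly a few more temporary stops. No new visits, data or analyses are needed.

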### **6.3.1 Potential drug-induced liver injury IMP discontinuation criteria**

Subjects with potential drug-induced liver injury (PDILI) must be assessed to determine if IMP must be discontinued. In addition, all concomitant medications and herbal supplements that are not medically necessary should also be discontinued.

The PDILI criteria below require immediate discontinuation of IMP:

- Subjects with either of the following:
  - ALT or AST  $\geq 8$ xULN
  - ALT or AST  $\geq 3$ xULN and coexisting total bilirubin  $\geq 2$ xULN
  - Subjects with ALT or AST  $\geq 3$ xULN who exhibit temporally associated symptoms of hepatitis or hypersensitivity. Hepatitis symptoms include fatigue, nausea, vomiting, right upper quadrant pain or tenderness. Hypersensitivity symptoms include fever (without clear alternative cause), rash, or eosinophilia (ie,  $>5\%$ ).

If a nondrug-related cause for the symptoms can be confirmed, these subjects may resume IMP administration after discussion with the responsible UCB physician, but only when the requirements for rechallenge with IMP as provided in [Section 12.2.1.2.1](#) are followed.

The PDILI criterion below allows for subjects to continue on IMP at the discretion of the Investigator.

- Subjects with ALT or AST  $\geq 5$ xULN and  $<8$ xULN, total bilirubin  $<2$ xULN, and no eosinophilia (ie,  $\leq 5\%$ ), with no fever, rash, or symptoms of hepatitis (eg, fatigue, nausea, vomiting, right upper quadrant pain or tenderness).

Evaluation of PDILI must be initiated as described in [Section 12.2.1](#) with repeat tests performed in 2 weeks. Upon retest, if ALT or AST values have reduced to  $<5$ xULN, the subject can continue with the study. However, if ALT or AST remains  $\geq 5$ xULN  $<8$ xULN after retest, IMP should be temporarily withheld and subject should undergo a repeat test in 2 weeks. The subject will continue to be monitored at least twice per week until values normalize, stabilize, or return to within baseline values. If ALT or AST values remain  $\geq 5$ xULN even after the second retest, then the subject should be permanently withdrawn from the study and should be followed for possible PDILI.

If subjects are unable to comply with the applicable monitoring schedule, IMP must be discontinued immediately.

Investigators should attempt to obtain information on subjects in the case of IMP discontinuation to complete the final evaluation. Subjects with PDILI should not be withdrawn from the study until investigation and monitoring are complete. All results of these evaluations and observations, as well as the reason(s) for IMP discontinuation and subject withdrawal (if applicable), must be recorded in the source documents. The eCRF must document the primary reason for IMP discontinuation.

## 7 STUDY TREATMENTS

### 7.1 Description of investigational medicinal products

The IMPs used in this study are bimekizumab, adalimumab, and placebo.

- Bimekizumab will be supplied in a 1mL PFS. Each single-use syringe contains bimekizumab drug substance at a nominal formulation of 160mg/mL in [REDACTED] mM sodium acetate, [REDACTED] mM glycine, and [REDACTED] % polysorbate 80 at pH [REDACTED] for sc injection.
- [REDACTED]
- [REDACTED]
- Placebo will be supplied as 0.9% sodium chloride aqueous solution (physiological saline, preservative free) of pharmacopoeia (US Pharmacopoeia/European Pharmacopoeia) quality in a 1mL PFS for sc injection.

Further details of the IMPs and their specifications will be provided in the IMP Handling Manual.

### 7.2 Treatments to be administered

The IMPs are to be administered in the clinic by unblinded study site staff. At all visits, only a single sc injection would be administered. Suitable areas for sc injections are the lateral abdominal wall and upper outer thigh. Injection sites should be rotated and injections should not be given in areas where the skin is tender, bruised, red, or hard.

An IMP Handling Manual will be provided to each site containing instructions regarding drug preparation and dosing.

The IMP dosing scheme is presented in [Table 7-1](#).

**Table 7-1: Dosing scheme**

Week	Baseline (first dose)	Double-Blind Treatment Period									Active Treatment-Blind Period																	
		2	4	6	8	10	12	14	16	18	20	22	24	26	28	30	32	34	36	38	40	42	44	46	48	50		
Bimekizumab 160mg sc Q4W	●	○	●	○	●	○	●	○	●	○	●	○	●	○	●	○	●	○	●	○	●	○	●	○	●	○	●	○ a
Adalimumab 40mg	▲	▲	▲	▲	▲	▲	▲	▲	▲	▲	▲	▲	▲	▲	▲	▲	▲	▲	▲	▲	▲	▲	▲	▲	▲	▲	▲	▲ a
Placebo	○	○	○	○	○	○	○	○	● b	○	●	○	●	○	●	○	●	○	●	○	●	○	●	○	●	○	●	○ a

Note: A bimekizumab 160mg Q4W dose injection is depicted by a black circle (●). A placebo injection is depicted by a white circle (○). An adalimumab 40mg injection is depicted by a black triangle (▲).

a Subjects that continue to the extension study will receive their final dose of IMP.

b Placebo subjects reallocated to bimekizumab 160mg sc Q4W (follow applicable schedules noted above).

### **7.3 Packaging**

The IMPs are manufactured, packaged, and labeled according to Good Manufacturing Practice guidelines and applicable laws or regulations. Investigational medicinal products will be suitably packaged in such a way as to protect the IMPs from deterioration during transport and storage.

### **7.4 Labeling**

Clinical drug supplies will be labeled in accordance with the current International Council for Harmonisation (ICH) guidelines on Good Clinical Practice (GCP) and Good Manufacturing Practice and will include any locally required statements. If necessary, labels will be translated into the local language.

### **7.5 Handling and storage requirements**

Investigational Medicinal Products must be stored under refrigerated conditions (2°C to 8°C) protected from light. The IMPs must not be frozen.

The Investigator (or designee) is responsible for the safe and proper storage of IMP at the site. Investigational medicinal product stored by the Investigator is to be kept in a secured area with limited access according to the storage conditions mentioned on the label.

Appropriate storage conditions must be ensured either by controlling the temperature (eg, room, refrigeration unit) or by completion of a temperature log in accordance with local requirements on a regular basis, showing actual and minimum/maximum temperatures reached over the time interval.

In case an out-of-range temperature is noted, it must be immediately reported as per instructions contained in the IMP Handling Manual.

### **7.6 Drug accountability**

A Drug Accountability form will be used to record IMP dispensing and return information on a by-subject basis and will serve as source documentation during the course of the study. Details of any IMP lost, damaged (due to breakage or wastage), not used, partially used, disposed of at the study site, or returned to the Sponsor or designee must also be recorded on the appropriate forms. All supplies and pharmacy documentation must be made available throughout the study for UCB (or designee) to review.

The packaging identifies each kit by a unique number that does not correlate to the contents and, therefore, does not unblind study site staff. Unblinded study staff will be responsible for preparation (eg, breaking tamper proof sticker on kit) of the clinical trial material, including recording the administration information in the source document.

The Investigator (or designee) is responsible for retaining all used, unused, and partially used containers of IMP until returned or destroyed.

The Investigator must assign some of the Investigator's duties for drug accountability at the study site to an appropriate pharmacist/designee.

The Investigator must ensure that the IMP is used only in accordance with the protocol.

Periodically, and/or after completion of the clinical phase of the study, all used (including empty containers)/partially used, unused, damaged, and/or expired IMP must be reconciled and either

---

destroyed at the site according to local laws, regulations, and UCB standard operating procedures (SOPs), or returned to UCB (or designee). Investigational medicinal product intended for the study cannot be used for any other purpose than that described in this protocol.

